### 4.2 Secondary outcomes

Carvedilol and placebo will be compared on the following outcomes:

- 1) Change from baseline in B-type natriuretic peptide (BNP)
- 2) Change from baseline in health-related quality of life (measured by EQ5D)

In addition, baseline BNP levels will be used to predict tolerance (yes, no) of a 6.25 mg dose of carvedilol during the run-in phase.

### **4.3 Tertiary outcomes**

Outcomes for exploratory analyses are:

- 1) The proportion of participants who consented to participate in and completed the home blood pressure and twenty-four hour ambulatory blood pressure sub-studies.
- 2) Intra-dialytic hypotension (no, yes), defined as a fall in systolic blood pressure of at least 20 mm Hg during or post dialysis relative to pre-dialysis associated with symptoms of hypotension (nausea/vomiting, cramps/pain in legs, dizzy/light headed, syncope/pre-syncope/loss of consciousness, chest or abdominal pain, other symptom) and requiring treatment for hypotension (head-low position, modification of ultrafiltration rate or target, infusion of any type of intravenous fluid specifically to treat hypotension, other treatment for hypotension).

### **4.4 Serious adverse events and adverse drug reactions**

Categories of serious adverse events (SAEs) and adverse drug reactions (ADRs) are:

- 1) SAEs classified according to World Health Organisation (WHO) categories (death, life-threatening, initial or prolonged hospitalisation, persistent or significant disability/incapacity, congenital anomaly, important medical event)
- 2) SAEs classified according to body system (cardiovascular, respiratory, gastrointestinal, dialysis complication, neurological, psychological, endocrine, pregnancy, haematology, skin, other)
- 3) SAE relationship to study medication (none, unlikely, possible, probable)
- 4) ADR severity (mild, moderate, severe, life-threatening)
- 5) ADR relationship to study medication (possible, probable)

## **5. SEQUENCE OF PLANNED ANALYSES**

### **5.1 Interim analyses**

SAEs and measures of study conduct and implementation by treatment group have been monitored on a regular basis by a Data and Safety Monitoring Board (DSMB). Only DSMB members and statisticians compiling closed-session reports for DSMB meetings have had access to un-blinded interim data and results. As this is a feasibility study, no interim efficacy analyses were planned or conducted.

### **5.2 Final analyses and reporting**

All final planned analyses identified in the protocol and in this SAP will be performed only after the last patient has completed the final end-of-study visit E6 and the database has been cleaned and locked. A blinded data review will be conducted by members of the Trial Management Committee (TMC) prior to locking the trial database. Treatment allocations will not be un-blinded and no un-blinded analyses will commence until this SAP has been

reviewed by the TMC and approved by the Chair of the TMC, the Director of the Australasian Kidney Trials Network (AKTN), and the Trial Statistician. Results from the final analyses will be reviewed by the TMC prior to completion of the FSR and subsequent manuscripts. Any post-hoc exploratory analyses performed to provide support for planned analyses but not identified in this SAP will be documented and reported in appendices to the FSR and clearly identified as unplanned analyses in the text of the FSR.

### **5.3 Changes to statistical information in the trial protocol**

This SAP does not contain any important changes to statistical information given in the final version of the trial protocol (6).

## **6. STATISTICAL ANALYSES**

### **6.1 Trial profile**

All patients who provided informed consent will be accounted for in the FSR. A CONSORT-style flow diagram will illustrate patient progression through the trial from initial screening for eligibility to completion of the final post-randomisation outcome assessments. Reasons for study withdrawal and major protocol deviations and violations will be documented.

### **6.2 Patient characteristics and baseline comparisons**

Demographic and other baseline characteristics will be summarised for participants who entered the run-in phase and by assigned treatment group for those who completed run-in and were randomised to carvedilol or placebo. Categorical variables will be summarised by frequencies and percentages. Percentages will be calculated according to the number of patients for whom data are available. Where values are missing, the denominator, which will be less than the number of patients assigned to the treatment group, will be reported either in the body or a footnote in the summary table. Continuous variables will be summarised by mean and standard deviation as well as quartiles.

The following baseline demographic and clinical characteristics will be presented: gender, age, ethnic origin (Caucasian, ATSI, Maori/Pacific Islander, Asian, Other, Unknown), height, weight, BMI, obesity (BMI <30, BMI ≥30), heart rate, blood pressure (systolic and diastolic), smoking status (never, former, current), primary cause of renal disease (diabetic nephropathy, hypertension/vascular, glomerulonephritis, reflux nephropathy, polycystic kidney disease, other, unknown), failing renal transplant (no, yes), dialysis treatment regimen (APD, CAPD, HD), diabetes mellitus (no, yes), hypertension (no, yes), ischaemic heart disease (no, yes), cardiac failure (no, yes), cerebrovascular disease (no, yes), peripheral arterial disease (no, yes), chronic lung disease (no, yes), quality of life, BNP, and a range of echocardiographic imaging measurements, including left ventricular end diastolic volume, left ventricular end diastolic dimension, left ventricular end systolic volume, left ventricular end systolic dimension, ejection fraction, stroke volume, left atrial size, E/A ratio, E/A duration, E/E' ratio, and global longitudinal strain.

## 6.3 Analysis of primary outcomes

### 6.3.1 Tolerability

Binomial proportions and 95% confidence intervals for the proportion of participants who completed run-in will be estimated using an intercept-only Generalised Linear Model from the binomial family with identity link function. Binomial proportions and 95% confidence intervals for randomised participants who drop out from carvedilol and placebo will be estimated using the same statistical model. Incidence rates for major adverse events (symptomatic hypotension and symptomatic bradycardia) in the randomised carvedilol and placebo groups will be estimated using intercept-only Poisson regression models.

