### **1.2 Study synopsis**

The BLOCADE trial is a feasibility study for a large multi-centre, randomised, placebo-controlled trial of the effectiveness of the beta-blocker carvedilol to reduce cardiovascular morbidity and mortality in high-risk patients receiving dialysis. The multi-centre feasibility study had a six week active run-in period during which all participants received carvedilol. After the run-in period participants who tolerated carvedilol were randomised 1:1 to receive carvedilol (experimental intervention) or placebo (control intervention).

The BLOCADE feasibility study began recruiting patients on 16 May 2011 and stopped recruiting on 28 February 2013 due to slow recruitment and lack of funds to continue recruiting participants. In total, 88 participants from 11 sites were consented into the study. Of these, 72 participants from 9 sites entered the run-in phase and 49 participants from 8 sites were randomised. The final end-of-study visit was conducted in June 2014. The central database is expected to be available for analysis by the end of June 2014.

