### 3.3. Sample size

The planned sample size was 150 patients to enter the run-in phase. This number was based on a confidence interval approach for estimating the proportion of patients who would tolerate carvedilol during the run-in phase. Assuming a tolerability of 70%, 150 patients would give 95% confidence limits of 62.5% and 77.5%. Due to slow recruitment and diminished funds, recruitment was prematurely stopped after 88 participants had been

consented into the study. Of these, 72 entered the run-in phase (48% of the target sample size).

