### **3.4 Treatment allocation**

Participants who tolerated a twice daily 6.25 mg dose of carvedilol by the end of the run-in phase were randomised 1:1 to one of the two treatment groups. Randomisation was conducted using an interactive voice response system (IVRS). The IVRS randomised patients by an adaptive allocation algorithm designed to minimise study site and dialysis modality (haemodialysis or peritoneal dialysis) imbalance within the two treatment groups.

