### 6.3.2 Sample size

Except for the proposed clinical endpoints, all proportions and 95% confidence intervals will be estimated as described above for tolerability outcome variables. Due to the small number of adjudicated clinical events, only counts will be presented for the proposed clinical outcomes.

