### 7.2 Statistical summary conventions

For tables, sample sizes for each treatment group will be presented as totals in the column header (N=xxx), where appropriate. Sample sizes shown with summary statistics are the number (n) of patients with non-missing values.

Summaries for categorical variables will include only categories that patients had a response in. Percentages corresponding to null categories (cells) will be suppressed. All summaries for continuous variables will include: N, mean, and SD. Other summaries (e.g. median, quartiles, 5%, 95% intervals, CV or %CV) will be used as appropriate. All percentages should be rounded and reported to a single decimal place (xx.x%). If percentages are reported as integers, percentages greater than 0% but <1% will be reported as <1%, whereas percentages greater than 99% but <100% will be reported as >99%. A percentage of 100% will be reported as 100%. No value of 0% should be reported. Any computation of percent that results in 0% is to be reported as a blank. Summaries that include p-values will report the p-value to three decimal places with a leading zero (0.001). P-values <0.001 will be reported as <0.001.

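### The SAP names no interval type for its identity-link binomial models, and the usual Wald default fails for primary proportions with few or no events

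*SAP*

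**What the plan says.** Section 6.3.1 states that run-in completion "will be estimated using an intercept-only Generalised Linear Model from the binomial family with identity link function". For drop-out in each randomised arm it adds: "Binomial proportions and 95% confidence intervals for randomised participants who drop out from carvedilol and placebo will be estimated using the same statistical model". Section 6.3.2 sets the clinical endpoints aside and then says "all proportions and 95% confidence intervals will be estimated as described above for tolerability outcome variables". That covers stopping study medication (outcome 2a), perceived need for a beta-blocker (2b) and withdrawal of consent (2c). Section 6.3.3 applies the same approach to the screening-eligibility and run-in entry proportions.

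Neither the kind of confidence interval nor a rule for sparse or zero counts is given. On reporting, Section 7.2 says: "Any computation of percent that results in 0% is to be reported as a blank".

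The denominators are known. Section 3.3 says "Of these, 72 entered the run-in phase", Section 1.2 says "49 participants from 8 sites were randomised", and by Section 3.4 participants "were randomised 1:1 to one of the two treatment groups".

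**The concern.** A model and a link do not fix an interval. An analyst who fits this model in standard software and takes the printed limits gets the symmetric Wald interval. With about 25 people and a handful of events, that interval can extend below zero, and its upper limit is too low. With no events it says nothing about uncertainty.

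The upper limit is the useful figure here. A planner of the larger trial wants to know how high drug-attributable drop-out or consent withdrawal could plausibly be. An upper limit that is too low makes these losses look better controlled than the data show. If no event occurs in an arm, the percentage is blanked under Section 7.2 and the model supplies no usable upper bound, so an informative feasibility result would appear without its uncertainty.

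**Working it through.** **Inputs.** 49 randomised (Section 1.2), 1:1 (Section 3.4), so about 24-25 per arm for outcomes 1b, 2a and 2b. Outcome 2c is defined without an arm split (Section 4.1), so n=49. Run-in n=72 (Section 3.3). Level 95%, taken as two-sided. True rates are not in the SAP; 2% to 30% is assumed.

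**The plan's own figure.** Section 3.3 gives 62.5% to 77.5% for 70% of 150. The Wald form p ± z·sqrt(p(1-p)/n) has standard error sqrt(0.7×0.3/150) = 0.0374. With z=1.96 it gives 62.7% to 77.3%; with z rounded to 2 it gives 62.5% to 77.5%, which matches. Wilson (62.2% to 76.8%) and Clopper-Pearson (62.0% to 77.2%) do not match. So the planning calculation was of Wald form.

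**The model's default interval.** An intercept-only identity-link binomial GLM, fitted to 1, 2, 3 and 4 of 25 and to 49 of 72, returned limits identical to the Wald formula. At 0 of 25 the fit gave a numerically zero-width interval; other software may fail to converge.

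**Limits at n=25.** Clopper-Pearson at zero events has upper limit 1 - 0.025^(1/25) = 13.7%.

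| Events | Wald | Wilson | Clopper-Pearson |
|---|---|---|---|
| 0 | 0 to 0 | 0 to 13.3% | 0 to 13.7% |
| 1 | -3.7% to 11.7% | 0.7% to 19.5% | 0.1% to 20.4% |
| 2 | -2.6% to 18.6% | 2.2% to 25.0% | 1.0% to 26.0% |
| 3 | -0.7% to 24.7% | 4.2% to 30.0% | 2.5% to 31.2% |
| 4 | 1.6% to 30.4% | 6.4% to 34.7% | 4.5% to 36.1% |

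At n=49 the Wald lower limit is also negative at 1 to 3 events (-1.9%, -1.5%, -0.6%).

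**Coverage.** This is the sum of binomial probabilities over the counts whose interval contains the true rate p. At n=25 and p=5%, those counts are 1 to 5, so coverage is P(X≤5) - P(X=0) = 0.9988 - 0.95^25 = 0.9988 - 0.2774 = 0.721. At p=2% they are 1 to 4, so coverage is 0.9999 - 0.98^25 = 0.9999 - 0.6035 = 0.396.

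| True rate | Wald, n=25 | Wald, n=49 |
|---|---|---|
| 2% | 39.6% | 62.8% |
| 5% | 72.1% | 91.6% |
| 8% | 87.3% | 90.7% |
| 10% | 91.9% | 87.2% |
| 15% | 89.9% | 93.8% |
| 20% | 88.4% | 93.4% |
| 30% | 94.9% | 93.3% |

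Results at n=24 are similar (38.4% at 2%, 70.7% at 5%). At n=25 and rates of 2-5%, Wilson covers 91-97% and Clopper-Pearson 98-99%.

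**Run-in completion.** Taking 49 of 72 as an illustration, Wald gives 57.3% to 78.8% and Clopper-Pearson 56.0% to 78.6%. Wald coverage at p=0.68 and n=72 is 93.6%.

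**The case against.** The strongest reply has four parts.

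- **The SAP never says Wald.** This is correct. A profile-likelihood interval from the same model stays in range: 0 to 7.4% at 0 of 25, and 0.2% to 16.5% at 1 of 25. What can be criticised is that no interval is named and that the usual default is poor for sparse counts. The Wald form of the planning limits makes the default more likely but does not settle it.
- **Nothing shows that events will be rare.** This also stands. A reader might infer that several of these proportions will have 0 to 3 events per arm, but the SAP gives no expected rates. Stopping study medication for any reason could well be common: at n=25 the chance of 0 to 3 events is 23% if the true rate is 20% and 3% if it is 30%. Rarity is more plausible for drug-attributable drop-out and consent withdrawal, but it remains an assumption.
- **The scope is limited.** A reader might infer that every primary proportion, or the precision on which the trial was sized, is compromised. The SAP does not support that. The 25 mg dose proportions use mixed-effects logistic regression, clinical endpoints are counts only, and hypotension and bradycardia use Poisson models. The sample size rests on run-in tolerability alone, which is barely affected.
- **A blank percentage need not hide a zero.** This stands in part. Section 7.2 also shows column totals and non-missing numbers, and Table 9 is planned as number and percent, so a count of zero may still be printed. The blank rule does not by itself make a zero result indistinguishable from missing data. It does remove the place where the estimate and its upper limit would stand.

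Section 6.3.2 shows that the authors recognised sparse data for the clinical endpoints, but no such safeguard covers the other proportions. Nor would the logit link that the document history shows being replaced be a cure: its interval stays within 0 to 1 but is likewise undefined at zero events.

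**Conclusion.** The point holds in a bounded form. The SAP fixes a model whose usual interval is unsuitable for sparse proportions, names no alternative and has no fallback. The outcomes at risk are 1b, 2a and 2b by arm and 2c pooled. Under-coverage is severe at n=25 for true rates up to about 5% (about 40% to 72%), modest at 8-20% (87-92%), and absent at 30%. For 2c at n=49 it is severe near 2% (63%) and mild at 5% (92%). This rests on two assumptions: that the software's default Wald limits are reported, and that some of these rates are low.

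The SAP ties no stated decision threshold to these limits and the main run-in estimate is sound, so this should be fixed but does not undermine the trial's central estimate.

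**What to change.** In Section 6.3.1, and by reference in 6.3.2 and 6.3.3, replace the identity-link GLM interval with a statement that each proportion is reported as x/n with a Wilson (or Clopper-Pearson) 95% confidence interval; choose one and name it. In Section 7.2, print zero results for primary and safety outcomes as 0 (0.0%) rather than a blank, so that a zero result appears with its upper limit.

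The cost is a change of wording and slightly wider intervals at low counts. At 1 of 25 the width goes from 15.4 points (Wald) to 18.8 (Wilson, 19.5 - 0.7) or 20.3 (Clopper-Pearson, 20.4 - 0.1). No new data are needed. Intervals for carvedilol-minus-placebo differences could be added but are optional and not part of this correction.

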### 6.3.2 Sample size

Except for the proposed clinical endpoints, all proportions and 95% confidence intervals will be estimated as described above for tolerability outcome variables. Due to the small number of adjudicated clinical events, only counts will be presented for the proposed clinical outcomes.

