## **1. INTRODUCTION**

### **1.1 Background**

Cardiovascular disease is a major cause of morbidity and mortality in patients receiving dialysis (9, 10). However, current therapeutic strategies rely on extrapolation from randomised controlled trials conducted in people without end-stage kidney disease (ESKD). The increasing evidence of benefit from beta-blockers in randomised controlled trials in the general population may lead to more patients with end-stage kidney disease being prescribed beta-blockers, despite the absence of evidence for their use in this group, making future recruitment for a trial such as this more difficult. Thus, the present time is considered a window of opportunity in which to study this question.

There is insufficient data on the tolerability of carvedilol in the ESKD population and a feasibility study is a key step in performing a large trial. In addition to information on tolerability, a feasibility study will provide logistical data and data relevant to sample size estimation that will help plan the study.

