## **2. STUDY OBJECTIVES**

### **2.1 Primary objectives**

The primary objective is to determine the feasibility and to inform the design of a larger clinical end-point study by measuring factors relevant to three aspects of planning a larger study:

- 1) Tolerability of carvedilol
- 2) Sample size for a clinical end-point study
- 3) Logistics of a larger study

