## 4. STUDY OUTCOME VARIABLES

### 4.1 Primary outcomes

A range of outcome measures were considered primary in order to assess the feasibility of a clinical end-point study with carvedilol as the intervention. These were:

- 1) Tolerability
  - a. The proportion of participants who finish the run-in phase on a twice daily dose of carvedilol of at least 6.25 mg. Participants who enter run-in but do not take any study medication will be counted among those who fail to finish run-in. Those who do not finish the run-in phase as defined above will be classified as a carvedilol-related failure or a failure for other reasons.
  - b. The proportion of participants randomised to carvedilol (placebo) that drop out due to any adverse event attributable to the study product.
  - c. The incidence of major adverse events of symptomatic hypotension and symptomatic bradycardia in participants randomised to carvedilol (placebo).
- 2) Sample size
  - a. The proportion of participants randomised to carvedilol (placebo) that cease study medication for any reason.
  - b. The Proportion of participants randomised to carvedilol (placebo) that are thought to require beta-blocker therapy after randomisation.
  - c. The proportion of participants who withdraw consent to participate in the study after randomisation.
  - d. Overall post-randomisation rate of the proposed composite primary outcome for the clinical end-point study (cardiovascular death, non-fatal myocardial infarction, non-fatal stroke, resuscitated cardiac arrest).
  - e. Overall post-randomisation rate of proposed secondary outcomes for the clinical end-point study (all-cause mortality, the composite primary outcome plus hospital admission for cardiovascular disease, total days in hospital, total days in hospital where cardiovascular disease is the main reason for admission).
- 3) Logistics
  - a. Recruitment rate (number per month)
  - b. The proportion of screened patients eligible for run-in.
  - c. The proportion of participants eligible for run-in who enter run-in.
  - d. The proportion of participants randomised to carvedilol (placebo) that are on a dose of 25 mg twice daily at each titration and follow-up visit.

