### 8.1 Planned tables

The following are planned summary tables:

- Table 1. Reasons screened patients were not consented into the study
- Table 2. Enrolment by study centre
- Table 3. Stratification variables by treatment group for randomised participants
- Table 4. Withdrawals, protocol deviations and violations during run-in
- Table 5. Withdrawals, protocol deviations and violations by treatment group
- Table 6. Demographic and clinical baseline characteristics for participants who entered run-in, overall and by successful completion of run-in (yes, no) [Table note indicating 16 consented participants did not enter run-in]
- Table 7. Demographic and clinical baseline characteristics by final run-in dose for all participants who entered run-in
- Table 8. Demographic and clinical baseline characteristics by treatment group for randomised participants
- Table 9. Number (percent) for primary outcomes of feasibility, sample size and logistics
- Table 10. Number of proposed primary and secondary outcomes for large clinical endpoint study
- Table 11. Intradialytic hypotensive episodes per dialysis session during run-in
- Table 12. Intradialytic hypotensive episodes per dialysis session overall and by treatment group for randomised participants
- Table 13. Number (percentage) of dialysis sessions during which an intradialytic hypotensive event occurred during run-in
- Table 14. Number (percentage) of dialysis sessions during which an intradialytic hypotensive episode occurred overall and by treatment group for randomised participants
- Table 15. SAEs and ADRs during run-in, overall and by successful completion of run-in (yes, no)
- Table 16. SAEs and ADRs by treatment group for randomised participants

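### Primary outcomes 2d and 2e are defined as event rates, but SAP section 6.3.2 and Table 10 plan only counts, with no person-time, rate or interval

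*SAP*

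**What the plan says.** Section 2.1 lists "Sample size for a clinical end-point study" as one of three aspects of the primary objective, and section 1.1 expects the study to supply "data relevant to sample size estimation".

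Section 4.1 turns this into five sample-size outcomes. Items 2a to 2c are proportions: stopping study medication, being thought to need a beta-blocker, and withdrawing consent. The other two are rates:

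- 2d: "Overall post-randomisation rate of the proposed composite primary outcome for the clinical end-point study"
- 2e: "Overall post-randomisation rate of proposed secondary outcomes for the clinical end-point study". These are all-cause mortality, the composite extended to cardiovascular admissions, total days in hospital, and days in hospital mainly for cardiovascular disease.

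Section 6.3.2 gives proportions with 95% confidence intervals to everything except the proposed clinical endpoints. For those it says: "Due to the small number of adjudicated clinical events, only counts will be presented for the proposed clinical outcomes". Section 8.1 agrees: "Table 10. Number of proposed primary and secondary outcomes for large clinical endpoint study". Table 9, for the other primary outcomes, carries numbers with percentages.

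**The concern.** A rate needs an amount of follow-up as its denominator, and the SAP plans none for 2d or 2e. Two outcomes called primary therefore have no planned estimator of the quantity that defines them.

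This matters because, for a given target effect and power, the person-time that an event-driven trial needs is inversely proportional to its event rate. A bare count does not account for unequal follow-up and does not show how wide the range of compatible rates is. For hospital days, a total without follow-up time is hard to interpret at all.

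**Working it through.** **1. Is there a figure in the plan to reproduce?** Not for this point: the SAP states no event count, person-time or event rate. Its only precision figure is for run-in tolerability (section 3.3: 70%, n = 150, limits 62.5% and 77.5%). That reproduces with two standard errors: 0.70 ± 2 × √(0.70 × 0.30/150) = 0.70 ± 0.075. Nothing below depends on it.

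**2. Definition against analysis.**

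| Outcome | Section 4.1 | Section 6.3 |
|---|---|---|
| 2a, 2b, 2c | proportion | proportion with 95% CI |
| 2d | rate, overall | count |
| 2e | rate, overall | count |
| 1c, symptomatic hypotension and bradycardia | incidence, by arm | Poisson incidence rate, by arm |

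The last row shows that the SAP already uses a Poisson rate elsewhere. It does so within each arm, about half of the 49 randomised, whereas 2d and 2e pool all 49 and so have the larger denominator.

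**3. Does the stated reason reach every endpoint?** It refers to adjudicated events. Section 3.5 says that the adjudicators reviewed possible cardiovascular events. All-cause mortality and total days in hospital are not clearly in that class, and days in hospital are not a rare-event count.

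**4. Available person-time.** Inputs: section 1.2, "49 participants from 8 sites were randomised"; section 3.1, titration of 6 weeks plus 4 more if needed, 12 months of follow-up, 4 weeks of down-titration; section 3.6, a final contact (E6) one month after study drug has ceased. With complete follow-up and 52.18 weeks per year:

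- 6 weeks + 12 months: 49 × (1 + 6/52.18) = 54.6 person-years
- 10 weeks + 12 months + 4 weeks: 49 × (1 + 14/52.18) = 62.1
- the same, with about 4 more weeks to E6: 49 × (1 + 18/52.18) = 65.9

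Losses, and stopping the clock at a first event, lower these. I assume 55 person-years (T) and show 50 and 60 as a range.

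**5. Exact Poisson limits.** For x events, the lower limit is χ²(0.025; 2x)/2 and the upper is χ²(0.975; 2x + 2)/2, each divided by T. The limits on the count are 0 to 3.689 for x = 0, 0.619 to 8.767 for x = 3, and 2.202 to 13.059 for x = 6. The values of x are assumptions. Rates per 100 person-years:

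| x | T = 50 | T = 55 | T = 60 | Upper/lower at fixed T |
|---|---|---|---|---|
| 0 | 0 (0 to 7.4) | 0 (0 to 6.7) | 0 (0 to 6.1) | – |
| 3 | 6.0 (1.2 to 17.5) | 5.5 (1.1 to 15.9) | 5.0 (1.0 to 14.6) | 14 |
| 6 | 12.0 (4.4 to 26.1) | 10.9 (4.0 to 23.7) | 10.0 (3.7 to 21.8) | 6 |

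The interval can be computed at every count, and even zero events gives an upper bound.

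**6. What a reader can recover from counts.** The crude risk is x/49. For 3 events it is 6.1% (Clopper-Pearson 95% CI 1.3% to 16.9%). That is a risk over unequal follow-up, not the rate in section 4.1, and the SAP plans no interval for it.

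**7. Meaning for planning.** The SAP gives no effect size or power for the large trial. Assuming a hazard ratio of 0.80, 90% power and two-sided 5%, the Schoenfeld formula gives 4 × (1.960 + 1.282)²/(ln 0.80)² ≈ 845 events. At 3 events in 55 person-years, 845/0.0545 is about 15,500 person-years. The interval limits translate to about 5,300 (upper) and 75,100 (lower).

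**The case against.** The other side has good points, and most of them limit the size of the finding.

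- **The change is disclosed.** Section 6.3.2 states the counts-only decision and its reason, and no treatment comparison is made on these endpoints, so no effect estimate is biased. This stands and lowers the severity.
- **The sample-size aim is not empty.** A reader might infer that it receives no usable estimate. The SAP does not support that: 2a, 2b and 2c are all estimated with 95% confidence intervals.
- **The rate is not out of reach.** A reader might also infer that the trial cannot yield an event rate. That goes too far: the number randomised and the scheduled follow-up are stated, so a crude risk or an approximate rate can be worked out. Section 7.2 puts N in table headers where appropriate, and the Preface allows supporting analyses labelled as unplanned. What is missing is a planned rate and interval.
- **The imprecision comes from the sample.** With 49 randomised, a 14-fold interval at 3 events could not size a large trial alone. This stands, but the width of that interval is itself a feasibility result worth showing.
- **Table 10 is judged by its title.** The table templates are in a separate document that is not at hand. However, the counts-only sentence in section 6.3.2 points the same way.

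**Conclusion.** The mismatch holds on the SAP's own text: outcomes 2d and 2e are defined as rates and analysed as counts. Followed as written, the plan does not report the quantity it names as primary, or its uncertainty. A small number of events makes a rate imprecise but does not prevent its estimation, and the stated reason does not clearly extend to deaths from any cause or to hospital days.

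The finding does not extend to 2a to 2c, and it does not mean that the rate cannot be derived from the trial's data. The 14-fold and 6-fold spans hold at any one fixed person-time and rest on assumed counts of 3 and 6. The rates themselves also depend on the assumed 55 person-years. Section 5.3 reports no important change from the protocol, which cannot be checked here. Severity: should be fixed. The repair improves transparency and matches the analysis to the outcome; it informs the size of the large trial but cannot fix it alone.

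**What to change.** In section 6.3.2, replace the counts-only sentence with wording such as:

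*For each proposed clinical event outcome, pooled over treatment groups, we will report the number of participants with an event, total person-years from randomisation to first event or last contact, and the rate per 100 person-years with an exact Poisson 95% confidence interval. For each hospital-days outcome we will report days per person-year with a participant-level 95% confidence interval.*

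State whether the period up to the E6 contact counts as follow-up, and name the method for the hospital-days interval. A bootstrap over participants is one option, but with skewed data in 49 people its coverage may be poor. Retitle Table 10 and add the matching columns.

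If the team prefers counts, the alternative is to redefine 2d and 2e as counts in section 4.1 and record any resulting departure from the protocol in section 5.3. That removes the inconsistency but gives up the planning rate.

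The cost is a short paragraph and a few table columns. It assumes that event and last-contact dates are recorded; the case report forms are not at hand to confirm this. The figures are pooled, so no treatment allocation is needed to produce them. The one drawback is that wide intervals will be on show.
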